4.9 Potential risks of study products and administration

Table 4-10 includes general risks of vaccine administration along with risks known from prior clinical studies of CH505TF gp120 products and similar envelope proteins with GLA-SE adjuvant.

Table 4-10 Summary of potential risks of study products and administration

Common	 Mild to moderate injection site pain, tenderness, erythema, or swelling/induration/edema A vaccine-induced positive HIV antibody test result
	· · · · · · · · · · · · · · · · · · ·
Less common	 Severe injection site pain or tenderness
	• Fever, chills, flu-like syndrome, arthralgia, rash, decreased appetite
	 Transient changes in clinical laboratory values
	• Injection site hematoma, bruising/ecchymosis, other transient lesions, itching, or bleeding related to the injection procedure
Uncommon or rare	 Severe localized injection site reaction, such as sterile abscess or secondary bacterial infection
	 Allergic reaction, including rash, urticaria, angioedema, bronchospasm, or anaphylaxis
	Muscle damage at the injection site
Theoretical risks	Autoimmune disease
	 Effects on a participant's response to an approved HIV vaccine administered in the future
	• Effects on susceptibility to HIV, if the participant is exposed to HIV
	 Effects on the course of HIV infection/disease, if the participant is infected with HIV

5 Objectives and endpoints

5.1 Primary objectives and endpoints

Primary objective 1:

To evaluate the safety and tolerability of HIV-1 CH505 transmitted/founder virus Env gp120 immunogen (CH505TF gp120) adjuvanted with Glucopyranosyl Lipid A - stable emulsion (GLA-SE) in healthy HIV-1 exposed uninfected (HEU) infants

Primary endpoint 1:

Local and systemic reactogenicity signs and symptoms, laboratory measures of safety, weight gain, and AEs and SAEs

Primary objective 2:

To determine whether vaccination with CH505TF gp120 adjuvanted with GLA-SE initiates B-cell lineages potentially capable of generating a broadly neutralizing antibody response

Primary endpoints 2:

Magnitude of HIV-1 Env gp120, CD4 binding site and V1V2-specific serum IgG binding antibodies, as assessed by BAMA two weeks after the 5th vaccination

Quantification and phenotypic characterization of peripheral B cells capable of binding HIV-1 Env gp120, the CD4 binding site (including differential binding to the I Δ 371 mutant) and the V1V2 binding site, as assessed by flow cytometry two weeks after the 3rd and 5th vaccinations

5.2 Secondary objectives and endpoints

Secondary objective 1:

To evaluate the effect of vaccination with CH505TF gp120 adjuvanted with GLA-SE on antibody responses to the South African Expanded Program on Immunization (EPI) schedule vaccinations

Secondary endpoint 1:

EPI vaccine-specific antibody responses, as assessed by Pediatric Vaccine Multiplex Assay (PVMA) 2 weeks after the 5th vaccination

Secondary objective 2:

To evaluate the ability of the vaccine regimen to elicit HIV-specific nAbs.

Secondary endpoint 2:

Magnitude and breadth of serum neutralization of vaccine-matched viral isolates, and viruses engineered to detect precursors of CD4 binding site and V1V2 antibodies 2 weeks after the 5th vaccination.

Secondary objective 3:

To measure Fc-mediated antibody effector functions

Secondary endpoints 3:

Response rate and magnitude of vaccine-elicited serum binding antibodies to FcR proteins, as assessed by BAMA 2 weeks after the 5th vaccination

Response rate and magnitude of serum Antibody-dependent cellular cytotoxicity (ADCC), as assessed by flow cytometry and/or luciferase assays 2 weeks after the 5th vaccination

Response rate and magnitude of serum Antibody-dependent cellular phagocytosis (ADCP), as assessed by flow cytometry 2 weeks after the 5th vaccination

5.3 Exploratory objectives

Exploratory objective 1:

To compare antibody and B cell responses generated in infants in response to CH505TF gp120 adjuvanted with GLA-SE with adults vaccinated with the same immunogen and same adjuvant on the same schedule (HVTN 115)

Exploratory objective 2:

To characterize B cell lineages and evaluate the amount of B-cell receptor somatic hypermutation

Exploratory objective 3:

To evaluate effects of maternal antibody in cord blood, serum/plasma, and breast milk on the humoral response of infants

Exploratory objective 4:

To evaluate additional vaccine-induced antibody effector functions such as Antibody-dependent neutrophil phagocytosis (ADNP) and/or Antibody dependent complement deposition (ADCD)

Exploratory objective 5:

To measure the kinetics and maturation of the polyclonal antibody response with biophysical measurements (eg, BioLayer Interferometry, Surface Plasmon Resonance)

Exploratory objective 6:

Evaluation of breast milk and fecal microbiome at birth and over time to explore the effect of the microbiome on the development of the immune system and on vaccine immunogenicity

Exploratory objective 7:

To use systems biology approaches (eg, high resolution flow cytometry. transcriptomics, proteomics, metabolomics and/or plasma cytokine/chemokine assessment) to determine whether the pre- and/or postvaccination systemic immune milieu is associated with vaccine immunogenicity.

Exploratory objective 8:

To further evaluate immunogenicity, additional assays may be performed based on the HVTN Lab Assay Algorithm

Exploratory objective 9:

To conduct analyses related to furthering the understanding of HIV, immunology, vaccines, and clinical trial conduct

6 Statistical considerations

6.1 Accrual and sample size calculations

Recruitment will target enrolling 38 healthy, HIV-uninfected infant participants born by Caesarian section to HIV-infected mothers (HIV exposed, uninfected infants). Although this study is proposed to be a direct comparison with HVTN 115, there are important differences in the populations that justify the inclusion of a larger placebo group. Specifically, we anticipate a higher rate of background severe adverse events in this population, as previous vaccine studies have determined a rate of 18% SAE in the placebo arm (74). This is markedly different from the background rate of severe adverse events in typical HVTN adult studies (~1-2%), supported by emerging safety data from the HVTN 115 study in adults (see Section 4.8.1). Therefore, we propose including a larger placebo group to ensure capacity for determining a safety signal in this vulnerable population.

There are both technical and logistical considerations that favor enrolling infants delivered via Caesarian section. From a technical standpoint, assessment of the evolution of antibodies requires an understanding of the baseline nature of B cells prior to vaccination. Standard assessment of antigen-specific B cell lineages requires several milliliters of blood, a volume that is unsafe in neonates. We intend to protect the participants of the study by performing baseline cellular assays on cord blood that would otherwise be discarded. For logistical reasons related to the study site, cord blood can only be collected during Caesarian sections.

Since enrollment of mother-infant pairs is concurrent with infants receiving the first study vaccination, all participants will be included in the safety analysis. However, for immunogenicity analyses, it is possible that data may be missing for various reasons, such as participants terminating from the study early, problems in shipping specimens, low cell viability of processed peripheral blood mononuclear cells (PBMCs), or high assay background. While the site staff report a historical rate of 10% missingness in infant studies conducted at the site, immunogenicity data from previous phase 1 and 1 phase 2a HVTN trials indicate that 25% is a reasonable estimate for the rate of missing data for the later timepoint (1 year). For this reason, the sample size calculations below account for 25% of enrolled participants having missing data for the primary immunogenicity endpoint.

6.1.1 Sample size calculations for safety

The goal of the safety evaluation for this study is to identify safety concerns associated with product administration. The ability of the study to identify SAEs can be expressed by the true event rate above which at least 1 event would likely be observed and the true event rate below which no events would likely be observed. Specifically, in the pooled Groups 3 and 5 (20 mcg CH505TF gp120 + 5 mcg GLA-SE vaccine arms) of the study (n = 18), there is 90% chance of

observing at least one event, if the true rate is 12% or more, and there is a 90% chance of observing no events, if the true rate is 0.58% or less. In the pooled placebo group of the study (n = 10), there is 90% chance of observing at least one event, if the true rate is 20% or more. There is a 90% chance of observing no events, if the true rate is 1% or less.

As a reference, in HVTN vaccine trials in Southern Africa from April 2008 through March 2018, about 1.7% of adult participants who received placebos experienced an SAE. Based on recent infant clinical trial studies including infants at the PHRU site, approximately 18% of infant participants who received placebos experienced an SAE (54).

Binomial probabilities of observing 0, 1 or more, and 2 or more events among arms of size 18 and 10 are presented in Table 6-1 for a range of possible true adverse event rates. These calculations provide a more complete picture of the sensitivity of this study design to identify potential safety problems with the vaccine.

Table 6-1 Probability (Pr) of observing 0 events, 1 or more events, and 2 or more events, among arms of size 18 and 10, for different true event rates

True event rate (%)	Pr(0/18)	Pr(1+/18)	Pr(2+/18)	Pr(0/10)	Pr(1+/10)	Pr(2+/10)
1	83.5	16.5	1.4	90.4	9.6	0.4
5	39.7	60.3	22.6	59.9	40.1	8.6
10	15	85	55	34.9	65.1	26.4
20	1.8	98.2	90.1	10.7	89.3	62.4
30	0.2	99.8	98.6	2.8	97.2	85.1
40	0	100	99.9	0.6	99.4	95.4
50	0	100	100	0.1	99.9	98.9
60	0	100	100	0	100	99.8
70	0	100	100	0	100	100
80	0	100	100	0	100	100
90	0	100	100	0	100	100

An alternative way of describing the statistical properties of the study design is in terms of the 95% confidence interval for the true rate of an adverse event based on the observed data. Table 6-2 shows the 2-sided 95% confidence intervals for the probability of an event based on an observed rate. Calculations are done using the score test method (75). If none of the 18 participants in Groups 3 and 5 experience a safety event, the 95% 2-sided upper confidence bound for the true rate of such events is 18%.

Table 6-2 Two-sided 95% confidence intervals based on observing a particular rate of safety endpoints for arms of size 18 and 10

01111	95%		
Observed event rate	Confidence interval (%)		
0/18	[0, 17.6]		
1/18	[1, 25.8]		
2/18	[3.1, 32.8]		
3/18	[5.8, 39.2]		
4/18	[9, 45.2]		
5/18	[12.5, 50.9]		
6/18	[16.3, 56.3]		
7/18	[20.3, 61.4]		
8/18	[24.6, 66.3]		
9/18	[29, 71]		
10/18	[33.7, 75.4]		
11/18	[38.6, 79.7]		
12/18	[43.7, 83.7]		
0/10	[0, 27, 9]		
0/10	[0, 27.8]		
1/10	[1.8, 40.4]		
2/10	[5.7, 51]		
3/10	[10.8, 60.3]		
4/10	[16.8, 68.7]		
5/10	[23.7, 76.3]		
6/10	[31.3, 83.2]		

6.1.2 Sample size calculations for immunogenicity

To address binding antibody endpoints, the analysis will descriptively summarize binding response positivity call rates to test superiority of IgG binding Ab responses for CH103-like CD4bs and V1V2 for comparisons versus zero using binomial exact tests with 5% type-I error rate each. Note that if in HIV-infected women, maternal antibodies that differentially bind to the CD4bs occur at a rate of 51% [estimated from n = 14 CAPRISA 002 women infected 2-3 years (76) and are transmitted to the infants, comparisons at early timepoints may be confounded by background positivity. Therefore, we have chosen the 2 weeks post 5th vaccination timepoint (~ one year) for the power calculation. By this time, both transplacental and breastmilk-associated antibodies (breast-feeding typically ceases at 6 months of age in the South Africa setting) are expected to have waned to below detectable levels, obviating the requirement to increase the placebo recipient sample size for a comparison with this high background rate. The following calculations assume a 25% rate of missing data to accommodate missingness at the 1-year timepoint.

The main goals of this trial regarding immunogenicity outcomes involve a preliminary estimation of rates of "response" (defined for Primary Endpoint 2 as initiation of either the CD4bs or the V1V2 B cell lineage) based on data from immune assays among vaccinees. No adjustment for multiple comparisons will be

made for the use of multiple assays. The precision with which the true response rate can be estimated from the observed data depends on the true underlying response rate and the sample size. Two-sided 95% confidence intervals for the response rate based on observing a rate of responses in the vaccinees is shown in Table 6-3. Calculations are done using the score test method (75). The n=13 assumes a 25% rate of missing immunogenicity data.

Table 6-3 Two-sided 95% confidence intervals for the true response rate based on observing a particular rate of responses in the vaccinees (n = 13)

No. of responses	Observed response rate (%)	95% Confidence interval
1/13	7.7	[1.4, 33.3]
2/13	15.4	[4.3, 42.2]
3/13	23.1	[8.2, 50.3]
4/13	30.8	[12.7, 57.6]
5/13	38.5	[17.7, 64.5]
6/13	46.2	[23.2, 70.9]
7/13	53.8	[29.1, 76.8]
8/13	61.5	[35.5, 82.3]
9/13	69.2	[42.4, 87.3]
10/13	76.9	[49.7, 91.8]
11/13	84.6	[57.8, 95.7]
12/13	92.3	[66.7, 98.6]
13/13	100	[77.2, 100]

As a reference, the range of the lineage initiate response rates seen in adult participants in HVTN 115, Part A was 30%-40%, varying by dose. The sample size of n = 13 yields greater than 90% power to detect a response if the true rate is 30% or greater.

Group 7 is not powered for a formal immunogenicity analysis but is instead intended to provide data for a cursory investigation of immunogenicity of a variant regimen with a lower protein dose: (5 mcg instead of 20 mcg of protein). After an expected loss of 25% of immunogenicity data, the sample sizes of n = 4 for this group is sufficient to detect an extreme loss of immunogenicity due to the lower dose. If 0 of 4 participants in this group is a responder, the upper end of the 95% confidence interval for the true response rate for that regimen is 49%.

As shown in Table 6-4, there is low power for a formal comparison of immunogenicity response rates between the Group 3 and 5 pooled vaccine arms of size n = 13 versus a pooled placebo arm of size n = 8 after accounting for missingness. The sizes of differences that the trial is powered to detect are around 70%. These calculations use a Fisher's exact 2-sided test with a Type I error rate of 0.05. There is insufficient power for a formal comparison across the vaccine regimens or between Group 7 and the pooled placebo group.

Table 6-4 Power for comparison of response rates between 2 pooled arms (n1 = 8, n2 = 13)

	-	in Arm 2 in order to detect a rence
True response rate Arm 1 (%)	80% power	90% power
0	64	73
10	79	87
20	89	95
30	96	-

6.1.3 Considerations for comparison of immunogenicity to adults in HVTN 115

To address Exploratory Objective 1 (comparison to adults), the analysis will descriptively summarize binding response positivity call rates, and test superiority of the frequency of differential memory B cell binding (to wild type vs mutant I Δ 371 CH505) and of the magnitude and breadth of the IgG binding Ab response to a panel of gp120 proteins using a two-sided Wilcoxon rank sum test with 5% type-I error rate per comparison. This exploratory objective involves a comparison across populations (infants versus adults, in different demographic settings). Since this factor is necessarily non-randomizable, these comparisons are of the "observational" category, in the sense that they do not share the statistical benefits of the randomized controlled clinical trial design. Specifically, while the "study" factor differentiates adults from infants, these cohorts differ in many other respects. Therefore, the interpretation of any differences observed will require more careful consideration of the potential confounding effects of measured and unmeasured differences across the populations besides the age of the vaccine recipient.

Immunogenicity in the HVTN 115 Part B vaccine recipients (n = 20 per group, n = 60 total), pooled with the corresponding dose group from Part A (n = 12) will be compared to immunogenicity in the HVTN 135 vaccine recipients. After an expected 15% of immunogenicity data missingness in HVTN 115 at the immunogenicity timepoint post 5th vaccination (at one year), sample sizes for comparisons across these study populations will be approximately n = 13 infants vs n = 27 (one HVTN 115 Part B arm, and one HVTN 115 Part A arm) or n = 61 (all 3 Part B vaccine arms, and 1 Part A arm). Comparisons are well-powered under this scenario for both binary responses and for comparisons of continuous responses (eg measuring antibody binding magnitudes). If the true response rate in adults is 30%, there is 80% power to detect a difference vs infant response rates if the true rate in infants is 82% or greater when comparing to n = 27 adults, and there is 80% power to detect a difference vs n = 61 adults when the true rate in infants exceeds 77%.

For continuous endpoints, there is 80% power to detect a difference across adult vs infant groups of 1.16 standard deviations (SDs) when considering n = 27 adults, and 1.04 SDs when considering n = 61 adults. As a point of reference,

using the mean and SD values from the HVTN 088 trial, the difference of 1.04 SD translates to a difference of 0.38 units of log10 binding magnitude; if one of the comparison groups has the same mean as was seen among non-negative values among vaccine recipients in the HVTN 088 trial (4.05 units), then after incorporating the expected 6% zero-valued (negative responder) measures, this corresponds to observing an increase or decrease in the overall mean from 3.78 in group 1 to 4.16 in group 2. These calculations assume a 15% loss-to-follow-up rate in HVTN 115 and a 25% rate in HVTN 135 and the (94%) response rate observed in the HVTN 088 vaccine recipients. The same approach will be used to test superiority of the magnitude of the IgG binding Ab response to each individual gp120 antigen in the panel.

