10.5 Endpoint assays: humoral

10.5.1 Binding antibody multiplex assay (BAMA)

HIV-1 Env binding IgG antibodies to the vaccine immunogens (EnvSeq-1 gp120 TF) will be assessed on serum/plasma samples from study participants taken at the primary immunogenicity timepoint and, due to the contributions of maternal antibody at birth, will be compared to matched samples from placebo controls. Conformational epitopes (eg, CD4BS specificities using differential binding to EnvSeq-1 gp120 TF compared to CH505 IΔ371 protein and sCD4 blocking) will be determined. Specimens from other timepoints as well as other HIV antigens (ie, other conformational epitopes and linear epitopes), IgA and antibody subclasses (IgG1, IgG2, IgG3, IgG4) may also be assayed based on the results of the initial assay. Cord blood, serum and/or breast milk samples may be tested to evaluate the effects of maternal antibodies.

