3 OBJECTIVES AND ENDPOINTS

3.1 Primary objectives and endpoints

Primary objective 1:

To evaluate the safety and tolerability of HIV-1 CH505 transmitted/founder virus Env gp120 immunogen (CH505TF gp120) adjuvanted with Glucopyranosyl Lipid A - stable emulsion (GLASE) in healthy HIV-1 exposed uninfected (HEU) infants

Primary endpoint 1:

Local and systemic reactogenicity signs and symptoms, laboratory measures of safety, weight gain, and AEs and SAEs

Primary objective 2:

To determine whether vaccination with CH505TF gp120 adjuvanted with GLA-SE initiates B-cell lineages potentially capable of generating a broadly neutralizing antibody response

Primary endpoints 2:

Magnitude of HIV-1 Env gp120, CD4 binding site and V1V2-specific serum IgG binding antibodies, as assessed by BAMA two weeks after the 5th vaccination

Quantification and phenotypic characterization of peripheral B cells capable of binding HIV-1 Env gp120, the CD4 binding site (including differential binding to the I Δ 371 mutant) and the V1V2 binding site, as assessed by flow cytometry two weeks after the 3rd and 5th vaccinations

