For quantitative assay data (eg, magnitudes and magnitude-breadth AUCs from the neutralizing antibody multiplex assay), graphical and tabular summaries of the distributions by antigen, treatment arm, and timepoint will be made. For all primary and secondary immunogenicity endpoints, box plots and plots of estimated reverse cumulative distribution curves will be used for graphical display of all of the study arms. Typically, the results will be shown for each vaccine arm and for the set of control arms pooled into one group.

Some immunologic assays have underlying continuous or count-type readout that are dichotomized into responder/nonresponder categories (eg, nAb multiplex assay positivity). If treatment arm differences for these assays are best summarized by a mixture model, then Lachenbruch's test statistic [4] will be used to evaluate the composite null hypothesis of equal response rates in the 2 arms and equal response distributions among responders in the 2 such arms. This test statistic equals the square of a binomial Z-statistic for comparing the response rates plus the square of a Wilcoxon statistic for comparing the response distributions in the subgroup of responders. A permutation procedure is used to obtain a 2-sided p-value. For estimation, differences in response rates between arms will be estimated using the methods described above, and in the subgroup of positive responders, differences in location parameters between arms will be estimated using the methods described above.

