9.3.1 List of Tables

- Summary table of BAMA response rate for infant participants by treatment group, study visit (v1/2 and v12), and antigen
- Summary statistics of Net MFI among all infant participants by treatment group, study visit (v1/2 and v12) and antigen
- Summary statistics of Net MFI among infant positive responders only by treatment group, study visit (v1/2 and v12), and antigen
- Summary statistics of BAMA AUC among all infant participants by treatment group, study visit (v12), and antigen
- Summary statistics of BAMA AUC among infant positive responders only by treatment group, study visit (v12), and antigen
- Summary statistics of differential binding among all infant participants by treatment group, study visit (v1/2 and v12) and antigen

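### The primary BAMA endpoint is a magnitude, but the plan leads with a response rate tested against zero and names no unconditional vaccine-placebo estimate or test of magnitude

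*Protocol*

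**What the plan says.** **Endpoint.** SAP 3.1, like Protocol 5.1, defines the first part of primary endpoint 2 as "Magnitude of HIV-1 Env gp120, CD4 binding site and V1V2-specific serum IgG binding antibodies, as assessed by BAMA two weeks after the 5th vaccination". SAP 9.3 measures it as net MFI or a titration result (EC50/AUC) and says both will be analysed on a log scale.

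**Planning.** Protocol 6.1.2 states: "To address binding antibody endpoints, the analysis will descriptively summarize binding response positivity call rates to test superiority of IgG binding Ab responses". The test is "for comparisons versus zero using binomial exact tests with 5% type-I error rate each". Tables 6-3 and 6-4 in that section concern response rates only. On the randomised comparison it says "there is low power for a formal comparison of immunogenicity response rates between the Group 3 and 5 pooled vaccine arms" and the pooled placebo arm.

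**Priority.** Protocol 6.4.4.1 and SAP 8.4.1 both put the one-sample comparison of response rates with zero first and give power as the reason. The SAP refers back to a power discussion that it does not itself contain.

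**Listed output.** For magnitude, SAP 9.3.1 gives items such as "Summary statistics of Net MFI among all infant participants by treatment group, study visit (v1/2 and v12) and antigen", with matching AUC tables. None is a between-arm estimate or test.

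**Other statements on magnitude.** Protocol 10.5.1 says that BAMA results "will be compared to matched samples from placebo controls", without a scale or method. SAP 8.4.1 has a conditional Lachenbruch two-part test and a normal-error model that applies when more than 20% of participants have missing values. It adds that "in the subgroup of positive responders, differences in location parameters between arms will be estimated using the methods described above".

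**The concern.** An analysis should estimate the quantity that the endpoint names. Here the endpoint is continuous, while the sizing and the prioritised test use a yes/no call from one arm. Infants of HIV-infected mothers start with maternal antibody, so the concurrent placebo group is the cleanest way to attribute antibody at month 13 to the vaccine. Protocol 10.5.1 gives that same reason for comparing with placebo.

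If the magnitude contrast is not fixed in advance, then its scale, its analysis set (all infants or responders only) and its method are open to choice after unblinding. The plan is more specific elsewhere. SAP 9.7.1 gives the secondary PVMA endpoint a vaccine-placebo geometric mean ratio with 95% CI. Protocol 6.1.3 gives the exploratory infant-adult comparison a two-sided Wilcoxon test and a detectable difference in SD units. The randomised contrast on the primary magnitude endpoint has neither.

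**Working it through.** **Inputs from the documents.** Evaluable n = 13 (Groups 3+5: 18 less 25%) and n = 8 (placebo: 10 less 25%); two-sided 5%; adult lineage response rate 30-40% (all Protocol 6.1.2). From Protocol 6.1.3, 1.04 SD equals 0.38 log10, so SD = 0.38/1.04 = 0.365 log10, and 6% of values are zero. That SD comes from another trial.

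**1. The plan's own figures**
- One-sample test against zero: one responder is enough to reject. Power at a 30% rate = 1 − 0.7^13 = 99.0%, consistent with the stated figure of more than 90%.
- Table 6-4, 80% column (printed 64/79/89/96): exact two-sided Fisher gives 54/74/83/90, and a continuity-corrected formula gives 65/78/88/95. The printed values fit an approximation and are conservative.
- Infant-adult differences of 1.16 SD (13 vs 27) and 1.04 SD (13 vs 61): simulated Wilcoxon power with 6% zeros is 78% for each, close to the stated 80%.

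**2. What the versus-zero test accepts.** If background positivity were 5% (assumed), the chance of at least one positive among 13 is 1 − 0.95^13 = 49%. At 1% it is 1 − 0.99^13 = 12%.

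**3. The missing contrast, 13 vs 8, when essentially all vaccinees shift**
- t-test: noncentrality = d × √(13×8/21) = 2.225d with 19 df. Power is 80% at d = 1.33 SD, which is 1.33 × 0.365 = 0.49 log10, or 3.1-fold.
- Wilcoxon, normal data: 80% at about 1.40 SD = 0.51 log10, or 3.2-fold.
- Wilcoxon with 6% zeros in each group, as in the infant-adult set-up: 80% at about 1.70 SD = 0.62 log10, or 4.2-fold.

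**4. The same contrast when a minority responds.** Here 35% of vaccinees shift and the rest look like placebo.
- Wilcoxon: 14% power for a 1.5 SD shift and 23% for 5.6 SD.
- Exact Fisher on rates, 35% against 0% placebo positivity: 28%. Across 30-40% responders: 17-43%.

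**5. Cost of dichotomising when everyone shifts.** For a 1.5 SD shift and 5% placebo positivity (assumed), 44% of vaccinees are positive. Wilcoxon power is 85% and Fisher power 38%.

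**6. Expected precision.** The 95% half-width on log10 is 2.093 × 0.365 × √(1/13 + 1/8) = 0.34, so the ratio would be known to within a factor of about 2.2 either way.

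**7. Whether the other provisions fill the gap**

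| Provision | Why it does not |
|---|---|
| Lachenbruch test | Used only if a mixture model is judged the best summary; gives a p-value, not an effect size |
| Normal-error model | Used only above 20% missing; names no contrast |
| Location difference | Responders only; points back to methods that are not set out |
| Protocol 10.5.1 | No scale, estimator or test |

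**The case against.** Leading with rates is a stated choice. Protocol 6.1.2 defines response for this endpoint as lineage initiation and sets preliminary estimation of rates as the goal. CD4 binding site specificity is itself a threshold call in SAP 9.3 (wild-type to mutant ratio of at least 2.5). Protocol 4.4.6 describes placebo comparisons as descriptive in a small trial. All of this stands, and it is why response rates should be kept. It does not reconcile a rate-based plan with an endpoint worded as a magnitude.

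A reader might infer that magnitude is never tested. The documents do not support that. The Lachenbruch test addresses magnitude among responders. The 13 vs 8 scenario is 21 of 28 infants, 25% missing, which would trigger the normal-error model. Box plots and reverse cumulative curves against pooled placebo are also planned.

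A reader might also infer that the randomised comparison is well powered on magnitude, so that the power reason for setting it aside falls away. That is not supported either. Protocol 6.1.3 uses that description only for infants versus adults, and neither document gives power for 13 vs 8 on magnitude. At the adult reference rate of 30-40%, the Wilcoxon test does no better than Fisher (step 4).

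**Conclusion.** The point holds as a specification gap on a primary endpoint: no unconditional, pre-specified vaccine-placebo estimate or test of BAMA magnitude is named. The prioritised analysis is a one-arm dichotomised test that a single positive call satisfies.

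The gain from the continuous scale depends on the response pattern. If essentially all vaccinees shift, as is plausible for overall gp120 binding, 13 vs 8 detects about a 3- to 4-fold difference with 80% power, and dichotomising can lose much of that. If only 30-40% shift, power is low on both scales, and the benefit is a pre-specified randomised estimate with its interval. The fold figures rest on an SD borrowed from another trial, which may not apply to infants or placebo recipients. The background positivity rates are assumptions.

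**What to change.** **SAP 9.3.1.** Add, as the randomised analysis of the BAMA magnitude endpoint, T3+T5 versus pooled placebo at visit 12 on log10 magnitude, in all infants with data, for the gp120, CD4bs and V1V2 antigens. Report a geometric mean ratio with 95% CI, as already planned for PVMA, supported by a two-sided Wilcoxon test. Fix one scale per antigen before unblinding: net MFI at the screening dilution, or AUC if all samples are titrated. This matters because SAP 9.3 lets titration depend on high binding being observed. State a floor for values at or below zero. Keep the response rates and differential-binding calls alongside.

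**SAP 8.4.1.** Name the method behind the location difference or refer to the new table.

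**Protocol 6.1.2.** State the detectable shift for 13 vs 8 (about 1.3 to 1.4 SD if essentially all respond, with the fold equivalents and the source of the SD), and that power is low on either scale at 30-40% responders. Make explicit that the low-power statement attached to Table 6-4 concerns response rates only.

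**Cost.** Wording and one more table, with no new samples or infants. The downside is a small-sample estimate with a wide interval.
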